**Drugs/Experimental Intervention:**

Subjects will receive 6 months combination drug therapy with a combination of low dose metformin and spironolactone.

Intervention – Metformin: The investigational pharmacy will distribute the metformin. The study dose will be 500 mg/tab orally BID, to be taken with food at breakfast and dinner. In order to improve tolerability of the regimen, the drug will be started sub-therapeutically. The first 4 days only ½ tablet will be taken with dinner and then increased to 1 tab for the next 3 days with dinner. The second week ½ tablet will be added to breakfast for four days and then the next 3 days the breakfast dose is increased to 1 tablet. After two weeks the subject will be on 500 mg BID from which time the 6- month intervention is counted. Long term use of metformin may lead to vitamin B12 deficiency. Therefore, vitamin B12 levels will be measured in the study and balanced diet is recommended.

Intervention - Spironolactone: The investigational pharmacy will distribute the spironolactone. The subject will take one tablet (50mg/tab orally QD) with breakfast once the metformin dose has been titrated up to 500 mg BID, approximately 2 weeks into the study. The 6-month intervention counts from the first dose of spironolactone taken.

**Observation and Measurements:**

Whole Body Insulin Sensitivity Index (WBISI): This determinant of insulin sensitivity has been validated against the euglycemic clamp as an accurate measure of insulin sensitivity in adolescents by the PI's former research group. The WBISI is calculated based on the area under the curve (AUC) for glucose and insulin during an oral glucose tolerance test. While the original WBISI (also known as Matsuda Index) requires a 3 hour glucose tolerance, calculating the index during a 2 hour glucose tolerance test has become common practice with good results.

Procedure: After an overnight fast, an 18-22 gauge intravenous catheter will be placed to allow easy access and minimize discomfort during repeated blood sampling. All hormone labs and baseline metabolic labs (including the 0- minute glucose and insulin) will be drawn immediately after placement of the indwelling catheter. The subject will be asked to drink 8 oz of a cola or orange flavored glucose solution (containing 75grams of glucose) to start the OGTT. Blood sampling during the OGTT will occur at the 30-, 60- and 120- minute time points and include blood for glucose and insulin so that the AUC can be calculated for WBISI. The baseline OGTT will be billed to insurance, the post intervention OGTT will be covered by study funds.

Ovarian Ultrasound: This ultrasound will be performed trans-abdominally through a full bladder on the same day of the OGTT in the Endocrine clinic office on Broadway. The radiology tech will use a portable ultrasound for patient convenience. The first ultrasound will be billed to insurance, the post intervention ultrasound will be covered by study funds.

Bio-impedance Scale: Body composition will be measured through the bio-impedance scale available in the Endocrine Clinic.

Depression Scale: The Hospital Anxiety and Depression (HADS) assessment will be used. The instrument has adequate psychometric properties and is considered a valid and reliable tool for screening adolescents for depression. A member of the MAPP research/clinical team has successfully implemented this tool in her examination of overweight insulin-resistant adolescents.

**Data Analysis:**

Primary Outcome: Insulin Sensitivity as assessed by the whole- body insulin sensitivity index (WBISI) also known as the Matsuda index. This is calculated from the Oral Glucose tolerance test and is a better parameter of insulin sensitivity than HOMA (based on fasting glucose and insulin values).

Power Analysis: Based on published research studies, a sample size of N = 20 patients per group, shows sufficient power. Metformin + Spironolactone group (n = 62): WBISI improved from 4.7+- 2.71 to 8.04 +- 4.03. When the sample size is 20, a paired *t*-test with a 0.05 two-sided significance level will have 93% power to detect the difference between a before treatment WBISI of 4.700 and after-treatment WBISI mean of 8.000, assuming that the standard deviation of change in WBISI is 4.0.

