### **Study Design:**

This is a single center clinical research study to obtain pilot data.

It is a non-controlled open label drug intervention study in a convenient sample of adolescent girls attending a PCOS clinic.

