### **Patients/Subjects:**

The sample will include 20 adolescent females (ages 13-21) of all ethnic backgrounds referred to the CMH adolescent PCOS program for evaluation and management of PCOS.

Patient risks and safeguards are extensively described in PROTECTION OF HUMAN SUBJECTS

Inclusion Criteria: Generally healthy; Meeting Androgen Excess Society (AES) diagnostic criteria of PCOS: Menstrual Dysfunction or PCO ovaries on ultrasound AND clinical or biochemical hyperandrogenism.

Normal liver and kidney function. No chronic illnesses except for stable, treated hypothyroidism.

Exclusion Criteria: Use of metformin and/or spironolactone within the last 6 months. Currently on either oral hormonal contraception or other forms of hormonal contraception such as Depo-ProveraR, NuvaRingR

Current or past pregnancy; Currently sexually active; Psychiatric disorder based on self/parental report; type 2 diabetes (blood glucose > 200mg/dl on OGTT); Anemia (Hct < 35); Baseline creatinine > 1.0 mg; Abnormal liver transaminases > 2 x the upper limit of normal range, potassium elevated outside the reference range (in non-hemolyzed blood sample).

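### Should the primary paired t-test be run on log WBISI instead of raw WBISI?

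*Combined protocol and SAP*

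**What the plan says.** The Data Analysis section names the primary outcome as "Insulin Sensitivity as assessed by the whole- body insulin sensitivity index (WBISI) also known as the Matsuda index" and gives no scale or transformation for it. The test appears only in the Power Analysis paragraph. That paragraph quotes a published combination-treatment group (n = 62) in which "WBISI improved from 4.7+- 2.71 to 8.04 +- 4.03". It then plans a paired t-test "with a 0.05 two-sided significance level will have 93% power". The effect is set by two planning values: "before treatment WBISI of 4.700 and after-treatment WBISI mean of 8.000". The spread rests on a single figure, for which no derivation is given: "assuming that the standard deviation of change in WBISI is 4.0". All these figures are in raw WBISI units.

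The section mentions no distribution check, rank-based alternative or geometric-mean summary. It reports no median, range, skewness or pre-post correlation from the published group. Under Patients/Subjects, "The sample will include 20 adolescent females". Under Study Design the trial is a single-center pilot: "It is a non-controlled open label drug intervention study".

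**The concern.** WBISI is positive by construction, yet its planning SDs are more than half its means. Between the two time points the SD rises by about half while the coefficient of variation (CV) hardly moves. A measure that varies in proportion to its level is usually analysed on the log scale. On the raw scale, a few girls with high insulin sensitivity and large absolute changes could carry much of the mean change and its variance.

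Precision on the primary endpoint would then be at stake in a sample of 20. The loss would matter most if the effect in adolescents is smaller than the planning effect, or if fewer than 20 girls complete both tests. Both are plausible. Background and Significance describes the combination study as one in adult women. Protection of Human Subjects discontinues girls who miss pregnancy tests or become sexually active. A raw-scale confidence interval could also miss unevenly on its two sides, which matters in a study meant to supply pilot estimates.

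**Working it through.** **1. The plan's own power.** Inputs from Power Analysis: n = 20, mean change 8.0 − 4.7 = 3.3, SD of change 4.0, two-sided 0.05. The noncentrality is (3.3/4.0) × √20 = 3.69 on 19 degrees of freedom. Exact power from the noncentral t is 93.8%, against the stated 93%. The figure reproduces.

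**2. What the planning SDs suggest.**
- CV before: 2.71/4.7 = 0.577. CV after: 4.03/8.04 = 0.501.
- Rise in SD: 4.03/2.71 = 1.49.
- Normal distributions with these values would put 4.1% (before) and 2.3% (after) of girls below zero.

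This fits right skew. It does not identify a lognormal shape, because other positive distributions can have the same means and SDs.

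**3. Implied correlation.** r = (2.71² + 4.03² − 4.0²)/(2 × 2.71 × 4.03) = 7.585/21.843 = 0.347.

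**4. Log-scale planning values if WBISI is lognormal.**
- Log variances: ln(1 + 0.577²) = 0.287 and ln(1 + 0.501²) = 0.224.
- Mean log change: ln(8.04/4.7) + (0.287 − 0.224)/2 = 0.537 + 0.031 = 0.57, a geometric mean ratio of about 1.77.
- Log covariance: ln(1 + 0.347 × 0.577 × 0.501) = 0.096.
- SD of log change: √(0.287 + 0.224 − 2 × 0.096) = 0.57.

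**5. Power on each scale, by assumed shape.** Simulated paired t-tests with n = 20, two-sided 0.05 and r = 0.347. For smaller effects the post-treatment SD must be assumed; the lognormal column interpolates it between the two published SDs. There were 60,000 trials per lognormal cell and 40,000 per gamma cell.

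| Mean change (share of plan) | Lognormal: raw / log | Gamma: raw / log |
|---|---|---|
| 3.3 (100%) | 95.7% / 98.8% (+3.1) | 95.5% / 96.0% (+0.5) |
| 2.5 (about 75%) | 84.0% / 91.9% (+7.9) | 82.9% / 84.5% (+1.6) |
| 2.0 (about 60%) | 69.3% / 79.7% (+10.4) | 66.9% / 69.0% (+2.1) |
| 1.65 (50%) | 55.0% / 65.3% (+10.3) | 52.2% / 54.1% (+1.9) |

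Other shapes:
- Weibull with the same means, SDs and r: the log test **loses** about 5 to 8 points.
- Truncated normal: a loss of about 8 to 15 points.
- Gamma matched only approximately to the means and SDs: a gain of about 1 to 6 points.

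The sign turns on how many girls have very low WBISI, because logs stretch low values apart. The documents do not give that information.

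**6. Validity of the raw test.**
- With no change and equal SDs, under lognormality, the raw test rejects about 4.5% of the time and the log test about 5.0%.
- At the planned effect under lognormality, the raw 95% interval lies wholly below the truth in 3.8% of trials and wholly above it in 1.4%. The total is 3.8 + 1.4 = 5.2%, so coverage is about 94.8%. The heavier tail understates the benefit.
- The t-test depends on the within-girl differences, not on the separate distributions. Their skewness is only about 0.5 to 0.8 under lognormality and 0.3 to 0.5 under gamma.

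**7. The target changes.** If the arithmetic mean stays the same but the CV falls from 0.577 to 0.50, the geometric mean still rises, by (0.287 − ln(1 + 0.50²))/2 = (0.287 − 0.223)/2 = 0.032 on the log scale. In simulated cells of that kind, the log test rejected 5.5% to 6.5% of the time. It is answering a different question from the mean difference on which the plan is built.

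**The case for a change.** The strongest case for a change is that the analysis scale is left open in an open-label study, that every summary figure in the plan fits right skew, and that fixing the scale takes a sentence and no extra patients. Under lognormality the gain is real. It reaches about 10 points at half to three-fifths of the planned effect. With 15 pairs at 75% of the effect, power is 72% raw against 81% log. The log-scale interval misses 2.5% on each side. The truncated-normal counter-example is also a strained one: matched to the baseline figures, it puts 3.5% of girls below a WBISI of 0.5, against 0.4% under gamma and under 0.01% under lognormality.

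Several parts of this stand. The scale is not stated outside the power calculation, right skew is the natural reading of the SDs, and the lognormal power figures are correct.

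What does not stand is a gain free of assumptions. Setting the truncated normal aside, gamma is also positive and right-skewed and leaves almost no gain, while Weibull reverses it. The smaller effects and the 15 pairs are assumptions too, because the documents give neither an adolescent effect nor a dropout rate. The uneven tails are a small defect in an interval whose overall coverage is right.

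**Conclusion.** No change to the plan follows. The planned test holds its level, its stated power is correct on its own inputs, and its interval covers at about the nominal rate even under the skew that prompted the concern. At the planned effect, the log scale offers about 3 points of power if WBISI is lognormal and about 0.5 if it is gamma, and it costs power under Weibull. The 8 to 10 points arise only if the shape is lognormal and the true effect is half to three-quarters of the planned one.

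Against that uncertain gain, the log scale replaces a change in WBISI units, the form in which the planning result is quoted, with a ratio of geometric means. Either choice is defensible for an uncontrolled pilot of 20 girls.

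What remains is missing detail: the scale is given only through the power calculation. An analyst would sensibly read that as a raw-scale paired t-test, inspect the differences, and report a log-scale ratio alongside as supportive. These figures rest on r = 0.347 and on assumed post-treatment SDs at smaller effects. The size of the lognormal gain shifts with both, but the test's validity is not in doubt.

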## **PROTECTION OF HUMAN SUBJECTS**

### **Subject Population Recruitment**

The study population will include adolescent females (age 13 to 21 years old) referred to Children's Mercy Adolescent PCOS Program. Prior to her first visit, the patient and her family will receive a letter about the voluntary research studies available through the PCOS Program. The patient may decline hearing about our research during her initial visit or any visits to the PCOS Program. If she declines participation, she will continue to receive standard of care in the Adolescent PCOS Program.

Medical Information Technology (MIT) will provide a list of qualified candidates. Potential subjects will be identified after a review of medical records through Cerner or other CMH sources (databases, billing records, pathology reports, admission logs). This may involve access to records by individuals not involved in the patient's care.

All subjects diagnosed with PCOS and treated at the CMH Diabetes Clinic will be identified by ICD-9 diagnostic codes. In accordance with 45 CFR 164.512(i)(1)(ii), (see <http://www.hhs.gov/hipaafaq/permitted/research/317.html>), qualifying patients will be identified initially by creation of a PCOS pre-screening log. This information is to be used solely for work preparatory to research (in this case the identification of qualifying subjects for targeted screening). No pre-screening information will be removed from CMH. This is necessary in order for the investigator, sub-investigator(s) and research coordinator(s) to effectively approach the entire clinic population for recruitment into the study. With the assistance of the IT department, all current CMH patients with type 1 diabetes [defined by (1) any patient visit tagged the diagnostic codes for PCOS from the prior 24 months will be identified. A password-protected pre-screening log of qualifying subjects and their next scheduled clinic appointment to the CMH diabetes center will be maintained to aid in subject identification. This will be updated quarterly. This will aid the key study personnel in efficiently and effectively attending particular clinic days/locations for optimal recruitment. The type 1 diabetes pre-screening log will contain subject names, medical record numbers and future clinic dates, as well as coordinator/investigator notes regarding eligibility. The entire screening log will be destroyed upon completion of targeted enrollment.

Qualified patients may also be identified by review of the daily clinic schedule, via review of Cerner data and billing records provided by MIT. Whether by phone or in person, only study personnel will give details about the study to subjects and families.

At their clinic visit, the study will be explained briefly, and subjects/parents will be asked whether or not they are interested in participating. All interested subjects and parents will have the study (including the risks and benefits) thoroughly explained using the written consent. They will be given copies of the consent to review without staff present, in order to allow them time to discuss with each other. They will be given an opportunity to ask additional questions after they have read the consent. If subject and parent agree to participate the appropriate child or adult consent will be signed.

Alternatively, subjects and parents will be given the opportunity to take consents home for further reading, discussion, and decision-making at a later date. These families may enroll at their next scheduled visit or another time convenient for them. No pressure will be placed on any subject or family to enroll. These families may be contacted by phone to ask if they want to participate.

Refusal to participate will be notated in the Research Prescreening Log. These patients will not be approached additional times for participation in this study.

A password-protected pre-screening log of qualifying subjects and their next scheduled clinic appointment to the CMH diabetes center will be maintained to aid in subject identification. This will aid the study personnel in efficiently and

effectively attending particular clinic days/locations for optimal recruitment. The PCOS pre-screening log will contain subject names, medical record number, date of birth, clinic visit date, clinic location, clinic provider appointment time as well as coordinator/investigator notes regarding eligibility. For those individuals not interested in participating, the minimum amount of PHI will be retained to ensure they are not approached again regarding participation in this study. Only their name and MRN will be retained. The remainder of the information will be deleted from the file. The entire screening log will be destroyed upon completion of targeted enrollment.

## **INFORMED CONSENT**

If the subject is between the ages of 13-21 on the date of the clinic appointment/study visit and parent agree to participate in the study, written informed consent/assent will be obtained before the extraction of any CMH EMR data.

Consent/assent will be obtained from research staff at the time of a routine clinical follow-up for T1DM. The study will again be explained to the family/patient and informed consent will be obtained in accordance with CMH Policy, IRB Protocols and Health and Human Services Regulation 45 CFR 46.116.

For those patients scheduled to see a provider participating the study, consent/assent and enrollment will be undertaken by a research assistant or alternative provider (and not the medical staff participating in the patient's clinical cares).

[figure not shown]
If the subject wishes to have more time to consider participating in the study, we will follow-up with a phone call and consent them over the phone at that time if they want to participate in the study.

## **DATA Collection**

Research material will be obtained through from their medical record for laboratory test results including OGTT, anthropometric measures, ultrasound data, vital signs, physical examination, including hirsutism score and birth history, medical history, family history and menstrual history will also be collected. Further materials include a depression score.

# VISIT FLOW

## **Risks and Inconveniences:**

### **1. Phlebotomy/OGTT**

While many patients with PCOS would potentially have an OGTT as part of their regular evaluation, most would not have repeat OGTT at 6 months. The OGTT will require venipuncture/i.v. insertion at the commencement of the OGTT. This can be painful may not succeed on first attempt. Bruising and tenderness can occur after venipuncture/i.v. insertion. Some also can feel faint or dizzy during venipuncture. After drinking the standard 75g of glucola on an empty stomach some patients may feel nauseated.

### **2. Ultrasound**

Transabdominal ultrasound evaluation of the ovaries requires a full bladder which may cause subjects discomfort as they are avoiding urination. Furthermore, pressing the ultrasound probe on a full bladder may be uncomfortable for some. There is no radiation or contrast involved in this test.

### **3. Metformin**

The main side effect of metformin is gastrointestinal discomfort such as flatulence, queasiness, and loose bowel movements. Metformin therapy can cause malabsorption of vitamin B12 in the distal ileum after long-term use for several years. Therefore, vitamin B12 levels will be monitored in the study. Subjects will be recommended to stay on a well-balanced diet. Lactic acidosis is a rare but potentially fatal metabolic consequence of metformin treatment. However nearly all reports of lactic acidosis are related to treatment in a patient in which metformin therapy was contraindicated due to renal and liver dysfunction. In the absence of contraindications lactic acidosis is not of concern in otherwise healthy people.

### **4. Spironolactone**

In general this drug is very well tolerated and poses no health risk in low dose. Given that spironolactone is a potassium-sparing diuretic it may elevate potassium levels in those with underlying kidney disease or excessive potassium intake. In the absence of contraindications like renal failure and in a presence of healthy well-balanced diet, spironolactone is unlikely to increase potassium levels outside the normal range. Should a subject not maintain a normal hydration status she may feel dizzy/lightheaded. This can be avoided by normal fluid intake. The main concern is the potential of this drug to under-virilize a male conceptus. Therefore, sexually active teenagers are excluded from the study. Nevertheless, every subject will be monitored with monthly urine pregnancy tests to assure that the study drug is not continued beyond the first two weeks post conception should an unexpected pregnancy occur. Study drugs will be immediately discontinued should a positive pregnancy test have occurred.

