Spironolactone has been used for decades as a potassium sparing diuretic and was found to have anti-androgenic effect in the 1970's . Its anti-androgenic effect is carried out through a dual mechanism of androgen receptor blockade, and via spironolactone's inhibition of 5-alpha reductase, thus reducing the conversion of testosterone to its biologically more potent metabolite, di-hydrotestosterone. The concern with studying spironolactone in adolescent girls has always been the potential effect of the drug to under-virilize a male embryo through transplacental exposure of the drug, should an unplanned pregnancy occur. However, unlike the widely prescribed OC, spironolactone does not pose a serious health risk (i.e thrombo-embolic events) to the patient herself  and therefore is the safer drug for the subject, especially if she is overweight and has a family history of thrombo-embolism events. Furthermore, a recent study in adolescent girls with hirsutism, demonstrated that a carefully designed study does not need to preclude adolescents from receiving anti-androgen therapy . In this study, adolescent girls with hirsutism were treated with the potent anti-androgen finasteride for 6 months and were not on oral contraceptive pills. In our proposed study, risk will be reduced by precluding sexually active teens from partaking in the study. Furthermore, all participants, even if not sexually active will be required to take a monthly pregnancy test for the duration of the study. This would likely safeguard against any inadvertent exposure of a male conceptus to spironolactone, as study drug would be discontinued immediately in the event of a positive pregnancy test. Lastly there has been a case report on a young woman treated with spironolactone (200-400mg daily) throughout each of her pregnancies due to Bartter Syndrome. In the case description she delivered two normal male infants and one normal female. At the time of the report one of the males had entered puberty at a physiologic time. While the teratogenic concern remains based on some, but not all animal studies carefully selected subjects and stringent protocol adherence should allow this very beneficial drug to be examined in adolescents with PCOS.

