## **Protection of Human Subjects**

All studies will be performed under the direct supervision of either the PI or co-investigators. Phlebotomy discomfort will be minimized by personnel skilled in venipuncture of children and obese patients.

Gastrointestinal side effects with metformin will be minimized by slow incremental dose increases over the course of two weeks. The PI has extensive experience with metformin and has used it in a clinical trial published in 2008. In terms of spironolactone treatment, potential subjects will be interviewed separately from their parents with our Adolescent Medicine co-investigators regarding their sexual activity. A patient who is sexually active will be excluded from participating in the study. Furthermore, subjects will be counseled on the potential teratogenic effects of spironolactone and the requirements of monthly pregnancy tests. Should a subject not comply with monthly pregnancy testing, then she will be discontinued from the study. Should a patient decide to become sexually active during the study, she will also be

discontinued from the study. Should a subject's pregnancy test turn positive then she will be discontinued of both intervention drugs. At that point the principal investigator will meet with the IRB to discuss recommendations in terms of following pregnancy outcome.

Prior to commencing spironolactone/metformin the PI will assess kidney functions and examine electrolytes with attention to potassium levels. Any abnormalities in one or both of these areas will prohibit entry into the trial. Subjects will be given the number of the principal investigator and the RA. They will also be given an emergency number that is available at all times through the section of Pediatric Endocrinology. All on call staff will be aware of the study.

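### Monthly pregnancy tests cannot guarantee that study drug stops within two weeks of conception; the schedule allows at least 28 to 31 days

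*Combined protocol and SAP*

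**What the plan says.** The first safeguard against fetal exposure is selection. Under Risks and Inconveniences, item 4 (Spironolactone), the protocol says: "Therefore, sexually active teenagers are excluded from the study". The Protection of Human Subjects section adds a withdrawal rule, beginning "Should a patient decide to become sexually active during the study, she will also be" and ending in discontinuation.

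Testing is the backup for a pregnancy that occurs anyway. Item 4 says each subject will be "monitored with monthly urine pregnancy tests to assure that the study drug is not continued beyond the first two weeks post conception", and that drug stops immediately on a positive result. Protection of Human Subjects gives two test-based triggers. On missed tests: "Should a subject not comply with monthly pregnancy testing, then she will be discontinued from the study". On a positive result, the subject whose "pregnancy test turn positive then she will be discontinued of both intervention drugs".

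Section B (Background and Significance) gives the same frequency: each participant "will be required to take a monthly pregnancy test for the duration of the study". Its claim for the safeguard is softer and carries no number: "This would likely safeguard against any inadvertent exposure of a male conceptus to spironolactone".

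**The concern.** Item 4 names a mechanism (monthly tests), a certainty and a limit (two weeks), and the mechanism cannot produce the limit. When sexual activity is not disclosed, the triggers left are a positive test and failure to test, and both run on the monthly schedule. No visible text ties tests to the menstrual cycle or adds earlier ones.

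The same item treats incomplete virilisation of a male fetus as the chief worry with spironolactone. Someone weighing that risk for girls and young women aged 13 to 21 would read a 14-day ceiling that the schedule does not support. Subjects are also to be counselled on teratogenicity, and that counselling should rest on a correct figure.

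**Working it through.** **Inputs**

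- Test interval T: monthly in all three sections. No day count or window is given, so T is taken as 28, 30 or 31 days.
- Stated limit: 14 days after conception (item 4).
- Delay from positive test to stopping: 0 days (item 4).
- Treatment period: six intervals, 6T days. Under Drugs/Experimental Intervention, "The 6-month intervention counts from the first dose of spironolactone taken".
- Detection lag D, from conception to a positive urine test: not in the documents. D = 0 is the case most favourable to the plan. D = 7, 10 and 14 are assumptions that show the range.
- Conception is taken as equally likely on any treatment day, with tests taken on schedule.

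**Step 1: can the 14 days be reproduced with no lag?**

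A conception u days after a negative test is found T − u days later. The maximum is T, the mean is T/2, and the share over 14 days is 1 − 14/T.

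- T = 28: maximum 28, mean 14.0, share 1 − 14/28 = 0.500
- T = 30: maximum 30, mean 15.0, share 1 − 14/30 = 0.533
- T = 31: maximum 31, mean 15.5, share 1 − 14/31 = 0.548

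The maximum is 28/14 = 2.0 to 31/14 = 2.2 times the stated limit. The 14-day figure is not reproduced as a maximum. It is close to the average.

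**Step 2: add an assumed lag**

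For a conception in the first five intervals, exposure runs evenly from D to D + T. In the sixth, drug ends at 6T in any case, so exposure runs from 0 to T. Hence:

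- maximum = T + D
- mean = [5(D + T/2) + T/2] / 6
- share over 14 days = {5[1 − (14 − D)/T] + [1 − 14/T]} / 6

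Example, T = 28 and D = 7: mean = (5 × 21 + 14)/6 = 19.8 days; share = (5 × 0.75 + 0.50)/6 = 0.708.

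| Lag D (days) | Maximum, T = 28 / 30 / 31 | Mean | Share over 14 days |
|---|---|---|---|
| 0 | 28 / 30 / 31 | 14.0 / 15.0 / 15.5 | 0.500 / 0.533 / 0.548 |
| 7 (assumed) | 35 / 37 / 38 | 19.8 / 20.8 / 21.3 | 0.708 / 0.728 / 0.737 |
| 10 (assumed) | 38 / 40 / 41 | 22.3 / 23.3 / 23.8 | 0.798 / 0.811 / 0.817 |
| 14 (assumed) | 42 / 44 / 45 | 25.7 / 26.7 / 27.2 | 0.917 / 0.922 / 0.925 |

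If the end of treatment is ignored, the shares are 75 to 77% at a 7-day lag, 86 to 87% at 10 days and 100% at 14 days. The maxima do not change. All shares are of such conceptions, not of participants.

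**Step 3: what interval would deliver 14 days?**

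T + D ≤ 14 gives T ≤ 14 − D: every 14 days with no lag, every 7 days at a 7-day lag, every 4 days at a 10-day lag. At a 14-day lag no interval works.

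**The case against.** The strongest reply is that the scenario is narrow. There are 20 subjects. They are interviewed apart from their parents, excluded if sexually active, counselled, and withdrawn if they become active. Withdrawal on disclosure stops drug without waiting for a test. This is right, and it limits the figures to undisclosed activity. But item 4 offers testing as the backup for exactly that case, and there the schedule alone sets the time to detection.

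Second, 28 to 31 days is a worst case: with no lag, 45 to 50% of conceptions fall within 14 days. That is also true, but an assurance is a statement about the worst case.

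Third, the lagged figures rest on assumed values and, for the shares, on how the end of treatment is handled. The conclusion does not need them, because the no-lag bound is enough.

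Fourth, the study flow chart is not visible and might time the tests differently. Three sections say monthly, so it is unlikely to rescue the claim. Nor can a missed period be relied on to prompt an earlier test, since menstrual dysfunction is one of the qualifying criteria under Patients/Subjects.

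Finally, the overstatement occurs once, and Section B words the same safeguard acceptably. This makes the correction small. It does not make the number right.

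**Conclusion.** The concern holds. With tests 28 to 31 days apart, the longest exposure in an undisclosed pregnancy is at least 28 to 31 days, not 14. This needs no outside figure, only the ordinary reading of monthly. With conception equally likely on any treatment day, 50 to 55% would exceed the stated limit even with a perfect test. Under an assumed lag of 7 to 14 days the maximum becomes 35 to 45 days, and about 71 to 92% exceed the limit when drug ends at six months.

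The defect is a mismatch between the schedule and the claim made for it. Monthly testing as a backup is not itself at fault. The point does not show that the trial is unsafe and does not touch the primary analysis. It should be corrected because it is a numerical safety statement about the risk the protocol ranks first for spironolactone.

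**What to change.** In item 4 (Spironolactone), replace the two-week assurance with the bound the schedule supports, for example:

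*Urine pregnancy tests will be done monthly, so that in an undisclosed pregnancy study drug would be stopped no later than one test interval (about a month) plus the time needed for the test to turn positive.*

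If a total is wanted, state the lag it assumes. A lag of up to 14 days gives 31 + 14 = 45 days, or about 6.5 weeks. Make the same change in the consent form if this wording appears there.

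The cost is one sentence and a less favourable figure, with no added procedure.

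Keeping the two-week limit means changing the schedule. Taking six months as 182 days and the present plan as about 6 tests per subject:

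- no lag, tests every 14 days: 182/14 = 13 per subject, (13 − 6) × 20 = 140 more tests in all
- assumed 7-day lag, weekly tests: 182/7 = 26 per subject, (26 − 6) × 20 = 400 more
- assumed 14-day lag: not achievable

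Restating the bound is the simpler choice.
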